5.6 STUDY VISIT PROCEDURES

5.6.1 Day -42 to Day -1 (Screening) Procedures

Patients will report to this visit fasted for 10 hours with only water allowed. The following screening procedures will be performed for all potential subjects at a visit (or visits) conducted within 42 days prior to dosing:

- Obtain informed consent.
- Collect demographic data.
- Review medical history.
- Assess inclusion/exclusion criteria.
- Measure height.
- Measure body weight.
- Conduct physical examination.
- Obtain 12-lead ECG (after subject has been supine for at least 5 minutes).
- Measure vital signs (including temperature, respiratory rate, and seated blood pressure and pulse).
- In patients with concomitant IBD, obtain colonoscopy report from eligible historical colonoscopy or undergo a colonoscopy procedure to obtain a new report if outside the 12-month window prior to MRCP.
- Obtain historical MRCP or ERCP for PSC diagnosis and dominant stricture assessment.
- Obtain new MRCP for baseline assessment.
- Record prior and concomitant medications.
- Perform Mayo Partial IBD Score.
- Obtain ~10-hour fasted clinical laboratory samples for the following:
 - Chemistry
 - Hematology
 - INR
 - Perinuclear anti-neutrophil cytoplasmic antibodies (p-ANCA)
 - CA19-9
 - Serum pregnancy test (all female subjects)
 - HIV antibody and hepatitis screen
- Obtain urine samples for the following:
 - Urinalysis (UA)
 - Selected drugs of abuse

5.6.2 Day 1 Procedures

Subjects will report to this visit fasted for 10 hours with only water allowed. The following procedures will be performed at the Day 1 Visit:

Pre-dose:

- Reassess inclusion/exclusion criteria.
- Measure body weight.
- Conduct physical examination.
- Obtain 12-lead ECG (after subject has been supine for at least 5 minutes).
- Measure vital signs (including temperature, respiratory rate, and seated blood pressure and pulse).
- Assess for concomitant medications.
- Assess for AEs from Screening period.
- Obtain 10-hour fasted clinical laboratory samples for the following:
 - Chemistry
 - Hematology
 - Lipids
 - C4 and serum bile acids
 - Vitamin D
 - INR
 - Enhanced liver fibrosis (ELF) panel
 - PK (pre-dose)
 - Anti-drug antibodies (ADAs)
 - Neutralizing antibodies (NAbs)
 - Exploratory biomarkers

■ [REDACTED]

- Obtain urine samples for the following:
 - Pregnancy test
 - UA
- Perform 5-D Pruritus Scale.
- Perform Mayo Partial IBD Score.
- Perform and then dispense Numeric Rating Scale (NRS) daily diary for Week 1 assessments.

In-clinic dosing:

- Confirm inclusion/exclusion criteria.
- Perform randomization.

- Dispense initial study-drug kit/diary (for recording of date/time of study-drug dosing).
- Provide study-drug SC self-administration instructions/training.
- Oversee subject study-drug SC self-administration.
- Perform local injection-site symptom assessment (LISSA) evaluation.

Before clinic discharge:

- Obtain 2-hour post-dose PK sample.
- Assess for AEs.
- Schedule subject for Week 1 visit.
- Instruct subjects to not self-administer their study drug until they are on-site.

5.6.3 Week 1 Procedures

Subjects will report to this visit fasted for 10 hours with only water allowed and undosed. The following procedures will be performed at the Week 1 visit:

Pre-dose:

- Measure vital signs (including temperature, respiratory rate, and seated blood pressure and pulse).
- Assess for concomitant medications.
- Assess for AEs.
- Perform LISSA evaluation.
- Obtain 10-hour fasted clinical laboratory samples for the following:
 - Chemistry
 - Hematology
 - PK (pre-dose)
 - ADAs
 - NAbs
 - Exploratory biomarkers
- Perform 5-D Pruritus Scale.
- Perform Mayo Partial IBD Score.
- Collect Week 1 NRS daily dairy.

Dosing:

- Collect old study-drug kit/diary and conduct reconciliation.
- Dispense new study-drug kit/diary.
- Oversee subject study-drug SC self-administration (from new kit).

Discharge (20 minutes after dosing):

- Assess for AEs.
- Schedule subject for Week 2 visit.
- Instruct subjects to not self-administer their study drug until they are on-site.

5.6.4 Week 2 Procedures

Subjects will report to this visit fasted for 10 hours with only water allowed and undosed. The following procedures will be performed at the Week 2 visit:

Pre-dose:

- Conduct physical examination.
- Measure vital signs (including temperature, respiratory rate, and seated blood pressure and pulse).
- Assess for concomitant medications.
- Assess for AEs.
- Obtain 10-hour fasted clinical laboratory samples for the following:
 - Chemistry
 - Hematology
 - PK (pre-dose)
 - ADAs
 - NAbs
 - Exploratory biomarkers
- Perform LISSA evaluation.
- Perform 5-D Pruritus Scale.
- Perform Mayo Partial IBD Score.
- Dispense NRS daily diary for Week 4 assessments.

Dosing:

- Collect old study-drug kit/diary and conduct reconciliation.
- Dispense new study-drug kit/diary.
- Oversee subject study-drug SC self-administration (from new kit).

Discharge (20 minutes after dosing):

- Assess for AEs.
- Schedule subject for Week 4 visit.
- Instruct subjects to not self-administer their study drug until they are on-site.

5.6.5 Week 4 Procedures

Subjects will report to this visit fasted for 10 hours with only water allowed and undosed. The following procedures will be performed at the Week 4 visit:

Pre-dose:

- Conduct physical examination.
- Measure body weight.
- Measure vital signs (including temperature, respiratory rate, and seated blood pressure and pulse).
- Assess for concomitant medications.
- Assess for AEs.
- Obtain 10-hour fasted clinical laboratory samples for the following:
 - Chemistry
 - Hematology
 - PK (pre-dose)
 - ADAs
 - NAbs
 - Exploratory biomarkers
- Obtain urine samples for UA.
- Perform LISSA evaluation.
- Perform 5-D Pruritus Scale.
- Perform Mayo Partial IBD Score.
- Collect Week 4 NRS daily diary.

Dosing:

- Collect old study-drug kit/diary and conduct reconciliation.
- Dispense new study-drug kit/diary.
- Oversee subject study-drug self-administration (from new kit).

Discharge (20 minutes after dosing):

- Assess for AEs.
- Schedule subject for Week 8 visit.
- Instruct subjects to not self-administer their study drug until they are on-site.

5.6.6 Week 8 Procedures

Subjects will report to this visit fasted for 10 hours with only water allowed and undosed. The following procedures will be performed at the Week 8 visit:

Pre-dose:

- Conduct physical exam.
- Measure body weight.
- Measure vital signs (including temperature, respiratory rate, and seated blood pressure and pulse).
- Assess for concomitant medications.
- Assess for AEs.
- Obtain 10-hour fasted clinical laboratory samples for the following:
 - Chemistry
 - Hematology
 - PK (pre-dose)
 - ADAs
 - NAbs
 - Exploratory biomarkers
- Perform LISSA evaluation.
- Perform 5-D Pruritus Scale.
- Perform Mayo Partial IBD Score.
- Dispense Week 12 NRS daily diary.

Dosing:

- Collect old study-drug kit/diary and conduct reconciliation.
- Dispense new study-drug kit/diary.
- Oversee subject study-drug SC self-administration (from new kit).

Discharge (20 minutes after dosing):

- Assess for AEs.
- Schedule subject for Week 12 (End of Treatment) visit.
- Instruct subjects to not self-administer their study drug until they are on-site.

5.6.7 Week 12 (End of Treatment)/Early Withdrawal Procedures

Subjects will report to this visit fasted for 10 hours with only water allowed and undosed. The following procedures will be performed at the Week 12/Early Withdrawal Visit:

Pre-dose:

- Measure body weight.
- Conduct physical examination.
- Obtain 12-lead ECG (after subject has been supine for at least 5 minutes).
- Measure vital signs (including temperature, respiratory rate, and seated blood pressure and pulse).
- Assess for concomitant medications.
- Assess for AEs.
- Obtain 10-hour fasted clinical laboratory samples for the following:
 - Chemistry
 - Hematology
 - Lipid panel
 - C4 and serum bile acids
 - Vitamin D
 - INR
 - ELF panel
 - Serum pregnancy test (all female subjects)
 - PK (pre-dose)
 - ADAs
 - NAbs
 - Exploratory biomarkers

█ ██████████

- Obtain urine sample for UA.
- Perform LISSA evaluation.
- Perform 5-D Pruritus Scale.
- Perform Mayo Partial IBD Score.
- Collect Week 12 NRS daily diary.

Dosing:

- Collect old study-drug kit/diary and conduct reconciliation.
- Oversee subject study-drug SC self-administration (from old kit) (not applicable for Early Withdrawal subjects).

Discharge:

(NOTE: Before-clinic-discharge assessments [PK sampling and AE recording evaluation] are not applicable for Early Withdrawal subjects. However, Early Withdrawal subjects should be scheduled for a 4-week Follow-up Visit.)

- Obtain 2-hour post-dose PK blood sample.
- Assess for AEs.
- Schedule subject for Week 16 (End of Study) Visit.

5.6.8 Week 16 (End of Study) Procedures

This visit will be performed 4 weeks after last dose of study medication. Subjects will report to this visit fasted for 10 hours with only water allowed. The following procedures will be performed at the Week 16 visit:

- Measure body weight.
- Conduct physical examination.
- Obtain 12-lead ECG (after subject has been supine for at least 5 minutes).
- Measure vital signs (including temperature, respiratory rate, and seated blood pressure and pulse).
- Record concomitant medications.
- Record AEs.
- Obtain 10-hour fasted clinical laboratory samples for the following:
 - Chemistry
 - Hematology
 - PK
 - Vitamin D
 - INR
 - Serum pregnancy test (all female subjects)
 - ADAs
 - NAbs
 - Exploratory biomarkers
- Obtain urine sample for UA.
- Perform LISSA evaluation.
- Perform 5-D Pruritus Scale.
- Perform Mayo Partial IBD Score.

5.7 CONCOMITANT MEDICATIONS

Any medication taken within 4 weeks prior to Screening and during the study period, as well as the reason for use, will be recorded in the source documents and the eCRFs.

Subjects should refrain from the use of any new prescription medications or products or change in the dose or frequency of existing therapies within 4 weeks prior to Day 1 until EOS. The Medical Monitor should be informed of any changes or addition of medications during this time period.

The following medications are prohibited from 4 weeks prior to Day 1 and through the end of treatment:

- Investigational agents, other than NGM282, or devices for any indication
- Known hepatotoxic agents
 - Concomitant medication can be screened at <http://livertox.nih.gov>
- Agents which can increase or decrease ALP
 - Patients on stable doses of a medication that may impact ALP for a minimum of 12 weeks can be considered for enrollment.
 - Medications which decrease ALP (such as UDCA, fibrates, bile acid resins) should also be screened for and not be started at any time point during the screening or study period.
- Agents used for the treatment of any condition listed in the exclusionary enrollment criteria (see [Section 5.2](#))
- Off-label use of therapies for PSC such as oral vancomycin, other antibiotics, or vedolizumab within 12 weeks of Screening through the EOS visit
- Any herbal medications other than standard vitamin supplements

In addition:

- Subjects taking medications for IBD must have been on a stable regimen of these medications for at least 12 weeks prior to Day 1 and should maintain if possible a stable dose during the study period.
- Subjects taking UDCA are eligible but must have been on stable doses of < 27 mg/kg/day for at least 12 weeks prior to their Screening. No significant dosage changes should be made during 8 weeks prior to Screening and a minimum 8-week washout period should occur prior to Screening if UDCA is stopped. Subjects not taking UDCA should not start it during the study period.

5.8 DIET AND ACTIVITY CONTROL

Subjects should maintain their normal level of physical activity, diet, and lifestyle throughout the entire study (i.e., will not begin a new exercise program or participate in any unusually strenuous physical exertion).

5.9 CLINICAL EVALUATIONS

5.9.1 Colonoscopy

Due to the high risk of colonic dysplasia in UC patients with PSC, a 2010 guideline from the AASLD recommends that patients with PSC and IBD undergo surveillance colonoscopy every 1–2 years from the time of diagnosis of PSC ([Chapman et al. 2010](#)). Patients with PSC without IBD should undergo surveillance colonoscopy every 5 years. If surveillance biopsies and flow cytometry show no evidence of dysplasia or aneuploidy, follow-up colonoscopy can be performed in 2–3 years. A possible exception would be those patients with >20 years' duration of colitis; in such patients it is reasonable to perform annual surveillance colonoscopy because of the high risk of dysplasia. If surveillance biopsies show no evidence of dysplasia, but flow cytometry is not available, a repeat colonoscopy is recommended annually. If surveillance biopsies reveal indefinite dysplasia, repeat surveillance colonoscopy is recommended every 6–12 months. If low-grade dysplasia is detected, a variety of options may be considered, including total colectomy. It would also be reasonable to repeat a surveillance colonoscopy within 3–6 months to confirm a diagnosis of low-grade dysplasia. If there are multiple sites of low-grade dysplasia or multiple inflammatory polyps that preclude adequate surveillance, colectomy should be recommended. However, if low-grade dysplasia is present in only one biopsy specimen, repeat surveillance colonoscopy in 6–12 months may also be considered. If high-grade dysplasia is detected, colectomy should be strongly recommended.

Because of the increased risk of dysplasia and colon cancer in PSC, all subjects with concomitant IBD in Study 15-0106 should have a colonoscopy with no evidence of dysplasia within 12 months of Screening ([Table 5.5-1](#)).

5.9.2 Magnetic Resonance Cholangiopancreatography

MRCP is a noninvasive technique for evaluating the intrahepatic and extrahepatic bile ducts and the pancreatic duct. Unlike conventional ERCP, MRCP does not require contrast material to be administered into the ductal system; thus, the morbidity associated with endoscopic procedures and contrast materials is avoided. However, MRCP does not permit interventions to be performed such as stone extraction, stent insertion, or biopsy. The optimal protocol to perform MRCP has not been defined; variation continues across centers. As a general rule, the protocol depends upon the specific magnetic resonance magnet being used, including its field strength (e.g., 1.5 versus 3T) and the manufacturer, as well as institutional experience and preferences. However, all acquisition protocols obtain heavily T2-weighted images as thick slabs and the images are reformatted in planes to optimize depiction of the extrahepatic ducts. Volume-rendered images may be used to depict the intra- and extrahepatic bile ducts.

In Study 15-0106, MRCP can be performed as one of the criteria for the diagnosis of PSC and will be performed in all subjects during Screening as a baseline assessment ([Table 5.5-1](#)).

5.9.3 Pharmacokinetic Blood Sample Collection and Processing

Blood samples for PK analysis of NGM282 levels will be collected before dosing on Day 1 and Weeks 1, 2, 4, 8, 12, and 16 (no dose administered) as outlined in the Schedule of Study Procedures ([Table 5.5-1](#)). On Day 1 and Week 12, an additional PK blood sample will be collected 2 hours post-dose.

Processing, storage, and shipping instructions for these PK blood samples will be presented in a separate Lab Manual.

5.9.4 Clinical Laboratory Assessments

Clinical laboratory evaluations including chemistry (fasted at least 10 hours), hematology, and UA will be collected as outlined in the Schedule of Study Procedures ([Table 5.5-1](#)).

Laboratory assessments of lipid panel (total cholesterol, LDL, HDL, and triglyceride) will be performed as outlined in the Schedule of Study Procedures ([Table 5.5-1](#)).

Laboratory assessments for C4 and serum bile acids will be performed as outlined in the Schedule of Study Procedures ([Table 5.5-1](#)).

Laboratory assessments for changes in bile-mediated absorption as measured by vitamin D and INR will be performed as outlined in the Schedule of Study Procedures ([Table 5.5-1](#)).

CA19-9 and p-ANCA will be collected at Screening as outlined in the Schedule of Study Procedures ([Table 5.5-1](#)).

ELF panel will be performed as outlined in the Schedule of Study Procedures ([Table 5.5-1](#)).

Hepatitis screen and HIV antibody screen will be performed at Screening.

A urine screen for drugs of abuse will be performed at Screening.

A stool sample will be collected at Day 1 and Week 12. If necessary, in order to obtain a sample, kits will be provided to patients for at-home collection and aliquoting, for return to clinic at Day 1 and Week 12 visits. Stool samples will be analyzed for calprotectin, microbiome (bacterial composition), and fecal fat content.

A serum qualitative pregnancy test (all female subjects) will be performed at Screening and Weeks 12 and 16. A urine pregnancy test (all female subjects) will be performed at Day 1.

Samples for analysis of ADAs, NAbs, and exploratory biomarkers will be collected as outlined in the Schedule of Study Procedures ([Table 5.5-1](#)). All NAb samples will be collected as scheduled and analyzed only if necessary based on ADA results.

Processing, storage, and shipping instructions for the above will be presented in a separate Lab Manual.

5.9.5 12-Lead Electrocardiograms

12-lead ECGs will be performed after the subject has been supine for at least 5 minutes, and as outlined in the Schedule of Study Procedures ([Table 5.5-1](#)).

5.9.6 Vital Signs

Vital signs (including temperature, respiratory rate, and seated blood pressure and pulse) will be obtained at Screening and at all study visits as outlined in the Schedule of Study Procedures ([Table 5.5-1](#)).

Seated blood pressure and pulse will be measured after the subject has been seated for at least 5 minutes.

5.9.7 Physical Examinations

A routine physical examination will be performed at Screening, Day 1, and Weeks 2, 4, 8, 12, and 16 as outlined in the Schedule of Study Procedures ([Table 5.5-1](#)). The physical examination may be performed by a physician, trained physician's assistant, or a nurse practitioner, as acceptable according to local regulation.

5.9.8 Weight

Subjects will be weighed at Screening, Day 1, and Weeks 4, 8, 12, and 16 as outlined in the Schedule of Study Procedures ([Table 5.5-1](#)).

5.9.9 Local Injection-Site Symptom Assessments

Injection-site evaluation will be made and documented (including photographs, as needed) by the PI or clinic staff using a LISSA ([Appendix A](#)).

The LISSA is to be administered pre-dose at Day 1 and Weeks 1, 2, 4, 8, 12, and 16 (End of Study) as outlined in the Schedule of Study Procedures ([Table 5.5-1](#)).

The instructions below are to be followed for the pre-dose LISSA:

- The injection-site area(s) should be examined for any injection-site reaction (ISR) at every visit.
- If a single ISR is observed, the LISSA should be used to rate that ISR.
- If multiple ISRs are observed, the LISSA should be used to rate the most severe ISR.
- The study visit note should document the total number of ISRs seen on examination.

The LISSA is intended to be a “snapshot” of the ISRs at the time of clinic assessment. The LISSA is not intended to capture ISR data (frequency, severity, duration, etc.) in between

clinic visits. As with any other potential AE, Investigator judgment should be used as to whether any ISR is recorded as an AE.

In addition to this, Mild to Severe Reactions (LISSA Grade 1–3) are reported as AEs at the discretion of the investigator unless standard serious adverse event (SAE) criteria are met and then must be reported as an SAE. Life-threatening (LISSA Grade 4) meet SAE criteria and must be reported as such.

LISSAs may be performed if necessary and as clinically indicated by the PI to capture ISRs outside of the routine scheduled assessment time points.

The 2007 FDA Toxicity Grading Scale ([Appendix A](#)) will be used to assess any ISRs ([U.S. Department of Health and Human Services 2007](#)). The documented record will include all of the symptoms, severity, and any local reaction (including pain, tenderness, redness, and swelling) and size of injection-site skin reactions identified and observed by the subject or clinic personnel. LISSA scores will be documented on the subject's eCRF.

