4 STUDY DESIGN

This is a multiple-center, randomized, double-blind, placebo-controlled, parallel-group study of NGM282 when administered for 12 weeks as a daily subcutaneous (SC) injection in patients with PSC. Approximately 60 subjects will be randomized across approximately 40–45 sites worldwide.

Patients will sign the Informed Consent Form at or prior to the Screening Visit and will undergo screening assessments to verify eligibility for the study (up to 6 weeks). Patients to be studied will have confirmed PSC as defined by an elevated ALP and either liver histology or cholangiography consistent with PSC. The presence of IBD is allowed as well as treatment with a stable regimen of biologic, immunosuppressant, or systemic corticosteroid therapy. UDCA therapy is allowed at stable doses for at least 12 weeks and < 27 mg/kg/day. Patients with decompensated cirrhosis, cholangiocarcinoma (diagnosed or suspected), acute cholangitis, or recently placed bile-duct stents will be excluded from this study. All subjects with concomitant IBD will be required to have had a colonoscopy within 12 months of Screening with no evidence of dysplasia. All subjects will undergo MRCP at Screening.

On Day 1, subjects will be randomized into one of the three treatment arms (NGM282 1 mg, NGM282 3 mg, or placebo) in a 1:1:1 ratio. The randomization will be stratified according to concurrent UDCA or no-UDCA status to ensure an even distribution across the three groups. Study-drug SC self-administration instructions and training will be provided to the subjects and a weekly study-drug kit will be dispensed. Treatment assignment will be blinded to the sites, subjects, Sponsor, and Medical Monitor throughout the study period.

The first dose (Day 1) and doses at Weeks 1, 2, 4, 8, and 12 will be self-administered in the clinic, with all other doses through Week 12 self-administered at home. Self-administration should occur at approximately the same time in the morning for every dose in both the clinic and at home.

Subjects will return to the clinic on Weeks 1, 2, 4, and 8 for on-treatment assessments and to receive weekly study-drug kits. Week 12 will be the End of Treatment (EOT) clinic visit. Subjects will return to the clinic at Week 16 (or 4 weeks after last dose) for an End of Study (EOS) follow-up visit.

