C4 = 7-alpha-hydroxy-4-cholesten-3-one; CA19-9 = carbohydrate antigen 19-9; ELF = enhanced liver fibrosis; EOS = End of Study; EOT = End of Treatment; ERCP = endoscopic retrograde cholangiopancreatography; HIV = human immunodeficiency virus; IBD = inflammatory bowel disease; INR = International Normalized Ratio; LISSA = local injection-site symptom assessment; MRCP = magnetic resonance cholangiopancreatography; NRS = Numeric Rating Scale; p-ANCA = perinuclear anti-neutrophil cytoplasmic antibodies; PK = pharmacokinetic; Wk = week.

^a There must be a minimum of 14 days between Screening and Day 1 visits for adequate separation of the repeated Chemistry (liver function tests) and INR assessments.

^b Colonoscopy will be performed only in patients with concomitant IBD and who do not have a colonoscopy available within 12 months of Screening.

^c MRCP will be performed in all subjects at Screening.

^d LISSA evaluations will be performed pre-dose for all on-treatment visits.

^e PK blood samples will be collected before subjects dose themselves in the clinic (pre-dose). At Day 1 and Week 12, an additional PK blood sample will be collected 2 hours post-dose.

^f NRS Itch/Fatigue will be completed as a daily diary during Day 1 and Study Weeks 1, 4, and 12. Diary will be dispensed at the study visit prior to the collection week.

^g Mayo Partial IBD Score will be collected in all patients, independent of whether they have IBD or not.

^h A second CA19-9 sample may be collected during the Screening period a minimum of 4 weeks from the original Screening sample in order to meet Inclusion Criteria 3g.

ⁱ A serum pregnancy test will be performed on all female subjects at Screening, Week 12, and Week 16. A urine pregnancy test will be performed on all female subjects at Day 1 (pre-dose).

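### Non-serious Grade 3 injection-site reactions become AEs only if the investigator chooses, so a severe related one may bypass the Grade 3 TEAE rules; the Day 1 LISSA timing is also contradictory

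*Protocol*

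**What the plan says.** **AE reporting.** Protocol 5.9.9 gives the investigator general latitude: "As with any other potential AE, Investigator judgment should be used as to whether any ISR is recorded as an AE". The following paragraph opens with the range mild to severe and continues: "Severe Reactions (LISSA Grade 1–3) are reported as AEs at the discretion of the investigator unless standard serious adverse event (SAE) criteria are met". Only the top grade is compulsory: "Life-threatening (LISSA Grade 4) meet SAE criteria and must be reported as such".

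Section 7.1 includes signs and symptoms among AEs and requires all AEs to be recorded from consent to the last follow-up, however they come to light. It also has the investigator grade AEs by CTCAE v4.03, and 7.2 has the investigator rate the causality of each AE. Section 5.3 stops a subject's treatment after one related Grade 3 TEAE. Section 4.1 stops the study at three related Grade 3 TEAEs in one CTCAE category.

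**Day 1 timing.** Section 5.9.9 states: "The LISSA is to be administered pre-dose at Day 1 and Weeks 1, 2, 4, 8, 12, and 16". Section 5.6.2 has no LISSA in its Day 1 pre-dose list. Its instruction, "Perform local injection-site symptom assessment (LISSA) evaluation", is the last item under in-clinic dosing, after the supervised first self-injection. Footnote d of Table 5.5-1, repeated in SAP 13.1, says: "LISSA evaluations will be performed pre-dose for all on-treatment visits".

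**The concern.** The safety rules in 4.1 and 5.3 work on TEAEs that carry two ratings, a CTCAE grade and a causality judgement. Both are made only once a finding has been entered as an AE. If entry is optional for a severe reaction, so are the two ratings, and the rules may not see an event they are meant to act on. Such an event would also be absent from the TEAE table by maximum CTCAE grade (SAP 8.1.3), though it would still appear in the injection-site table (SAP 8.7).

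The timing conflict concerns data quality. Before the first injection there can be no study-drug reaction. If some of the roughly 40–45 sites follow 5.9.9 and others 5.6.2, the Day 1 row of the injection-site table (protocol 8.10.7, SAP 8.7) would mix scores that cannot show a drug reaction with genuine first-dose scores.

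**Working it through.** The plan gives no figure to reproduce, so the check sets the texts side by side and counts where that helps.

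**Part 1: path from a severe reaction to the safety rules**

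1. Is a LISSA Grade 3 reaction an AE under 7.1? Appendix A defines Grade 3 pain as pain that needs a narcotic or stops daily activity. That is an untoward symptom and falls within 7.1, so 7.1 requires it to be recorded.
2. Does 5.9.9 require it? No. For Grades 1–3 the only exception to the investigator's discretion is an event that meets SAE criteria. A non-serious Grade 3 reaction may therefore stay as a LISSA score alone.
3. What does it then lack? The CTCAE v4.03 grade (7.1) and the causality rating (7.2), since both attach to AEs. Neither 4.1 nor 5.3 refers to the LISSA score.
4. What does one unrecorded event change, assuming it would have been rated CTCAE Grade 3 and related?

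Section 5.3 has a threshold of 1, so one unrecorded event is enough to miss the rule for that subject. Section 4.1 has a threshold of 3. With k related Grade 3 events of the category already on record:

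| k on record | Count with the missing event (k + 1) | Effect of the omission |
|---|---|---|
| 0 | 1 | none, below 3 either way |
| 1 | 2 | none, below 3 either way |
| 2 | 3 | rule should be met but is missed |
| 3 or more | 4 or more | none, rule already met |

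The documents give no expected frequency of LISSA Grade 3 reactions, so no rate is estimated. The only related information is in protocol 2.4: in the 28-day PBC trial, all but one of the reported reactions were mild. The present trial doses daily for 12 weeks.

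**Part 2: Day 1 timing**

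- Scheduled LISSA time points: Day 1 and Weeks 1, 2, 4, 8, 12 and 16, which is 7. Affected: 1 (Day 1).
- Texts that name Day 1 as pre-dose: 1 (5.9.9).
- Texts that list it after the injection: 1 (5.6.2).
- Texts that do not settle it: 2 (footnote d of Table 5.5-1 and its copy in SAP 13.1). The footnote speaks of on-treatment visits, and Section 4 uses that term for later visits: "Subjects will return to the clinic on Weeks 1, 2, 4, and 8 for on-treatment assessments". If Day 1 is included, the footnote contradicts 5.6.2; if not, it is silent on Day 1.
- The 5.9.9 sentence also calls for a pre-dose assessment at Week 16, although 5.9.3 notes that no dose is given then. Sections 5.9.11 (5-D Pruritus) and 5.9.12 (Mayo score) use the same sentence pattern, and for those scales a pre-dose Day 1 baseline makes sense. The wording looks like a standard sentence that was not adapted to the LISSA.

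**The case against.** **The wording may be consistent.** Section 5.9.9 first presents the discretion as the usual judgement on whether a finding is an AE, after which 7.1 would require recording. That reading fits the first sentence. It does not fit the next paragraph, which extends discretion expressly to severe reactions and excepts only serious ones.

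**The scales differ.** The LISSA uses the 2007 FDA vaccine scale, AEs use CTCAE v4.03, and no mapping is given. A LISSA Grade 3 score can arise from redness wider than 10 cm alone, so it need not be a CTCAE Grade 3 event. This stands, and it is why the claim is only that a reaction may fail to reach the rules.

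**Other routes exist.** AEs are checked at every visit from Day 1, and both before dosing and at discharge at Weeks 1 to 8. Medications are recorded with their reason (5.7), clinical review includes LISSAs (8.10), a DMC is in place (10.7), and the sponsor and the investigator keep discretion (4.1, 5.4). These make a missed event unlikely. None of them removes the option that 5.9.9 gives, or requires the two ratings for a reaction the investigator has left as a LISSA score.

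**The gain is limited.** The LISSA is a snapshot at clinic visits while most doses are taken at home, and the same investigator would still set grade and causality. This is correct: the gain is that both ratings must be made and documented for the severe reactions seen in clinic.

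**On timing,** sites may simply follow the visit list in 5.6.2, and a pre-dose check could record existing redness or tenderness. Both are fair. The texts still disagree, and a single Day 1 assessment cannot satisfy both.

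**Conclusion.** Both parts hold, and both are minor. Section 5.9.9 makes AE reporting of non-serious severe injection-site reactions optional, against 7.1, and so leaves open whether such a reaction receives the ratings on which 5.3 and 4.1 depend. One omission matters for 5.3; for 4.1 it matters only at a count of exactly two. This assumes a reaction that the investigator would have graded CTCAE 3 and judged related. How often that would happen cannot be derived from the documents, and the PBC experience suggests seldom.

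The Day 1 contradiction affects one of seven LISSA time points in a descriptive table on which no decision rests. The AE check before discharge and unscheduled LISSAs can still pick up first-dose reactions. Neither point touches the primary endpoint or its analysis.

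**What to change.** 1. In 5.9.9, require every LISSA Grade 3 reaction to be recorded as an AE with its own CTCAE v4.03 grade and causality rating. Keep discretion for Grades 1–2. State that the CTCAE grade, not the LISSA grade, feeds 5.3 and 4.1. No threshold moves.
2. Set the Day 1 LISSA after dosing and before discharge, pre-dose at later on-treatment visits, and without a dosing reference at Week 16. Change 5.9.9 and footnote d in both Table 5.5-1 and SAP 13.1. Section 5.6.2 already fits.

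The cost is a few sentences, two footnotes and an eCRF completion note. No visit or sample is added, since subjects already stay for the 2-hour PK draw on Day 1. The downside is slightly more injection-site AEs on record; any that the investigator grades CTCAE 3 and related will lead to discontinuation, as 5.3 already requires.
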